In-person visits: Participant's 2 in-person visits will occur in private rooms at the Montefiore/Einstein ICTR Clinical Research Center. At the baseline visit, study staff will describe the study and obtain written informed consent. Tracking forms as well as agreements to release medical, pharmacy, and PMP records will be completed. Participants will receive a refillable debit card for compensation. At all in-person visits, we will administer questionnaires, and collect blood and urine samples. Participants will receive \$27.50 for each in-person visit.

Phone or web visits will occur weekly over 14 weeks and include brief (5-7 minute) questionnaires administered by study staff over the phone or completed on-line. A total of 15 visits will occur, the first at baseline, when participants can be trained on how to complete it, and then one at the end of each week of the follow-up period. Participants will receive \$3 on debit cards after completing each phone or web-based questionnaire.

Blood draws will occur at week 0 and 14 in-person visits. They will measure VL, CD4 count, pro- and anti-inflammatory cytokines. Participants will be compensated an additional \$15 for each visit in which there is a blood draw.

Main independent variable will be the soft gel capsule product dispensed at Vireo, including a 1) high THC capsule, or 2) high CBD capsule. Other key independent variables will be cumulative THC and CBD taken (weeks 3-14, continuous measures).

Main outcome variables: Our primary outcome is pain severity, measured via the BPI severity scale (ordinal variable), as recommended by a committee of international pain experts.⁹² It is an 11-point (0-10) numerical rating scale of pain intensity, where 0 is 'No pain' and 10 is 'Pain as

bad as you can imagine'. Participants will complete the BPI severity scale in each phone visit (baseline and at each weekly visit).

Pro- (TNF α , IL-1 β , IL-6) and *anti-* (IL-4, IL-10) *inflammatory cytokines (secondary outcomes;* 0, 14 week *blood draws*) will be measured with Luminex assay and reported as picograms per mm 3 (continuous measure).

Adverse events (secondary outcomes) will be ARV adherence (AIDS Clinical Trial Group [ACTG] Adherence Interview,^{93,108} Adherence Visual Analog Scale [VAS; weekly]),⁹⁴ VL suppression (blood draws at 0, 14 weeks; copies/mL); and psychological symptoms—depression (CES-D; 0 and 14 weeks),⁹⁵ anxiety (GAD-7; 0 and 14 weeks),^{96,94,97,109}

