Other key outcome variables will be alternative pain measures (painDETECT,⁸⁴ pain catastrophizing⁹⁸).

Other measures that have strong associations with medical cannabis use or neurologic pain will be measured, including biological sex, substance use, quality of life, HIV risk behaviors, symptoms of post-traumatic stress disorder (PTSD), insomnia and medical comorbidities (Table 8).

3) Study Population

3.A. Sample size and power

determination. For our primary analysis (Aim 1), we based our power analysis on proportion of participants with clinically significant change in BPI pain severity scale (30% reduction) in each condition.^{8,48} We will recruit 100 participants in total; we anticipate that approximately 50 will use high THC soft gel

capsules and 50 will use high CBD soft gel capsules. Conservatively assuming 15% attrition in each arm, 42 participants will be in each arm. Because the individual-level intra-class correlation coefficient (ICC) associated with change in pain severity over time is unknown, we conducted simulation studies with varying ICC values, i.e., 0.2, 0.3, and 0.4. We present power calculations for pain severity in Table 9. Based on prior studies,^{47,48} we predict that 40% of those using high THC capsules will experience clinically significant reduction in pain and 20% of those using high CBD capsules will experience clinically significant reduction in pain.¹¹⁰ We will have 84% power at a significance level of 5% (two-tailed test) to detect a 20% difference in proportion of participants who achieve clinically significant reduction in pain during the follow-up period between high THC soft-gel capsules (40%) and high CBD (20%) soft gel capsules. We will have greater power to detect a larger difference or when ICC is lower.

For analyses with continuous dependent variables (Aim 2-3), a sample size of 42 participants/arm will allow us to have >90% power to detect a moderate effect size (i.e., Cohen's $d=0.5$) under a more stringent condition (ICC=0.4). We will have greater power when the effect size is larger or when ICC is lower.

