Aim 1: Examine how medical cannabis use affects self-reported pain. H1: The effect of medical cannabis use on self-reported pain-severity will differ by THC/CBD content. The primary outcome will be change in BPI pain severity scale (ordinal variable, 0-10; measured at baseline and weekly for 14 weeks). A clinically significant change is 30% reduction in BPI pain severity scale.⁹² Secondary measures will include BPI pain interference scale and neuropathic pain (painDETECT). We will compare the proportion of participants who achieve clinically significant change in pain at 14 weeks between those who use high THC soft gel capsules and those who use high CBD soft gel capsules. BPI pain interference scale and painDETECT will be compared between those using high THC vs high CBD as well. We will use mixed-effects logistic regression to test the effect of study arm on pain relief across the course of the study. Results will be adjusted for covariates associated with the outcomes of interest on bivariate testing. We will repeat this model using alternative measures of medical cannabis (cumulative dose of THC and CBD).

Aim 2: Examine how medical cannabis use affects pro- and anti-inflammatory cytokines. H2: Medical cannabis that has higher THC content will have greater reduction in pro-inflammatory

cytokines ($TNF\alpha$, $IL-6$). *H3: Medical cannabis that has higher CBD content will have greater increase in anti-inflammatory cytokines ($IL-4$, $IL-10$).* We will examine how pro- and anti-inflammatory cytokines measured at 0 and 14 weeks change in participants using high THC products versus high CBD products. We will use mixed-effects linear regression analyses to examine intervention and time effects as well as intervention-by-time interactions. This approach is appropriate in the event that the pro- and anti-inflammatory cytokine data show a non-normal distribution. We will repeat this model using alternative measures of medical cannabis (cumulative dose of THC and CBD). We will adjust for other chronic conditions that may lead to change in inflammatory cytokines, such as obesity, cardiovascular disease, and diabetes.

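### For the two-visit cytokine change test of Aim 2, ICC=0.4 is not shown to be the stringent case, power does not rise as ICC falls, and the >90% figure is not reached

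*Combined protocol and SAP*

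**What the plan says.** Section 3.A gives one power statement for all continuous outcomes of Aims 2-3: "a sample size of 42 participants/arm will allow us to have >90% power" for a moderate standardised effect of 0.5, "under a more stringent condition (ICC=0.4". It then adds "We will have greater power when the effect size is larger or when ICC is lower". The SD that serves as the unit of Cohen's d is not named.

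On measurement, section 2.C states "Blood draws will occur at week 0 and 14 in-person visits". The footnote to the measures table likewise puts blood tests and in-person questionnaires at weeks 0 and 14 only. Cytokines, VL, CES-D and GAD-7 therefore have two values per person. The adherence visual analogue scale is weekly.

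On analysis, section 7.A states for Aim 2: "We will use mixed-effects linear regression analyses to examine intervention and time effects as well as intervention-by-time interactions". H2 and H3 concern a greater decrease or a greater increase, so they are hypotheses about change. For Aim 3, section 7.A specifies mixed-effects linear regression without naming an interaction, and H4 is worded in terms of levels.

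**The concern.** The ICC acts in opposite directions on two kinds of comparison. When many repeated values are averaged into one level per person, a high ICC means that the repeats add little information, so power falls as ICC rises. When a person's later value is compared with their own baseline, a high ICC means that the stable part of the measurement cancels, so the change is less noisy.

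Section 3.A applies the first rule to outcomes whose planned Aim 2 test is of the second kind. Section 3.A calls the ICC for change in pain unknown, and the documents give none for cytokines. A reader is told that a lower value can only help. If that is wrong, restating the power at ICC=0.4 alone would still leave that value labelled as the hard case. A null cytokine result could then be given more weight than the design supports.

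**Working it through.** **Inputs.** Section 3.A: 42 analysed per arm (50 × 0.85 = 42.5), d=0.5, ICC=0.4. The two-sided 5% level is stated there for Aim 1 ("at a significance level of 5% (two-tailed test") and is assumed to carry over. The values 0.2 and 0.3 appear only for the Aim 1 simulations and are used here as an illustrative range. Power is from the noncentral t with 82 df (81 with baseline adjustment) unless noted. SD is the single-visit SD, set to 1.

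**Step 1: reproduce the stated figure.** For the mean of m repeated values per person, the variance is (1+(m−1)·ICC)/m. With m=14 and ICC=0.4 this is 6.2/14 = 0.443, so the SD is 0.665. The noncentrality is 0.5/(0.665·√(2/42)) = 3.44 and power is 0.925. At ICC 0.3 and 0.2, power is 0.969 and 0.994. Both the >90% and the stated direction are reproduced. At ICC=0.4 at least 7 values per person are needed to reach 90% (0.901 with m=7).

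The same 14-measure structure comes close to Table 9. With effective n = 42·14/(1+13·ICC) per arm and a normal approximation for two proportions, 40% against 20% gives 0.979, 0.927 and 0.858 at ICC 0.2, 0.3 and 0.4. Table 9 has 0.97, 0.91 and 0.84.

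**Step 2: the Aim 2 test.** With two visits and complete data, intervention-by-time is the difference between arms in mean change from week 0 to week 14. Var(change) = 2·(1−ICC), so SE = √(4(1−ICC)/42).

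- ICC 0.4: SE = √(2.4/42) = 0.239; 0.5/0.239 = 2.09; power 0.543
- ICC 0.3: SE = √(2.8/42) = 0.258; 0.5/0.258 = 1.94; power 0.482
- ICC 0.2: SE = √(3.2/42) = 0.276; 0.5/0.276 = 1.81; power 0.433

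A simulation of 20,000 trials per ICC gave 0.537, 0.479 and 0.432. The effect detectable with 80% power, (1.96+0.842)·SE, is d=0.67 at ICC 0.4 and d=0.77 at ICC 0.2.

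**Step 3: other units for d.**

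- SDs of change: the ICC cancels. Noncentrality = 0.5/√(2/42) = 2.29; power 0.62 at any ICC.
- Within-person SDs: the SD of change is √2 of these units. Noncentrality = 0.5/(√2·√(2/42)) = 1.62; power 0.36 at any ICC.

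**Step 4: other analyses of a two-visit outcome** (d in single-visit SDs).

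| Comparison | SE | ICC 0.2 | ICC 0.3 | ICC 0.4 |
|---|---|---|---|---|
| Change, week 0 to 14 | √(4(1−ICC)/42) | 0.433 | 0.482 | 0.543 |
| Week 14 adjusted for week 0 | √(2(1−ICC²)/42) | 0.637 | 0.660 | 0.695 |
| Week 14 alone | √(2/42) | 0.62 | 0.62 | 0.62 |
| Mean of weeks 0 and 14 | √((1+ICC)/42) | 0.832 | 0.802 | 0.772 |

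Only the last row follows the plan's direction. It averages a pre-exposure value into the effect and still falls short of 90%.

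**The case against.** The strongest reply is that the reversal depends on a unit the plan does not state. That stands: with d in SDs of change or within-person SDs, ICC=0.4 is neither the best nor the worst case. A reader might infer that power necessarily falls as ICC falls in any change test, and the documents do not support so general a claim. The reply does not rescue the plan's sentence, because power is then flat in ICC and still well below 90%.

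Second, a reader might extend the point to all of Aims 2-3. Section 7.A names intervention-by-time only for Aim 2. For Aim 3 it names no such term, and H4 speaks of levels. A week 14 comparison alone would not depend on ICC, and a mean over both visits would follow the plan's direction. The weekly adherence scale, compared as an average level, also follows it. So for VL, CES-D and GAD-7 the point is conditional on an analysis of change or of week 14 adjusted for week 0.

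Third, it is tempting to say that the plan's worst case is the best of its own three ICC values. Those three values were set for pain severity in Aim 1. The Aims 2-3 statement names only 0.4, so there is no stated ICC range for cytokines.

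Fourth, the spread across ICC (0.43 to 0.54) is small beside the gap from >90% to 0.54, and both problems probably share one root. That is fair, and it argues for correcting them together. Nothing here disputes the corresponding Aim 1 statement: Table 9 is consistent with about 14 repeated measures.

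**Conclusion.** The point holds for Aim 2. For cytokines measured at weeks 0 and 14 and tested by intervention-by-time, power is not greater at a lower ICC under any of the three units of d examined, and ICC=0.4 cannot be called the stringent case. With d in single-visit SDs the direction reverses: about 0.54 at ICC 0.4 and 0.43 at ICC 0.2. In the other two units power is about 0.62 or 0.36 throughout. None approaches 90%. That the Aim 1 weekly structure was carried over to two-visit outcomes is an inference from the numerical match; the documents do not say so.

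The result assumes 42 analysed per arm, a two-sided 5% level, equal variances at the two visits and complete pairs. For the two-visit Aim 3 outcomes the conclusion is conditional on the analysis chosen. These are secondary aims, and the sample size rests on Aim 1. The correction therefore concerns what power the plan states, not how the study is run.

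**What to change.** In section 3.A:

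1. Limit the description of ICC=0.4 as the stringent case, and the statement that lower ICC raises power, to weekly outcomes compared as levels.
2. For outcomes measured at weeks 0 and 14, state which SD is the unit of d.
3. Replace >90% with the power of the planned week 0 to 14 change test over a range of ICC, for example 0.2 to 0.4, labelled as an assumption because no cytokine ICC is given. In single-visit SD units at d=0.5 this is about 0.43, 0.48 and 0.54, with the lowest ICC as the stringent case.
4. In section 7.A, name the Aim 3 contrast for VL, CES-D and GAD-7 so that its power can be stated on the same basis.

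Make this change together with any correction of the >90% figure, since one recalculation serves both. The cost is rewording the power paragraph, one clarifying sentence for Aim 3, and a less favourable stated power for secondary aims. Recruitment, visits and data collection are unaffected.

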Cannabis use may lead to worse HIV outcomes, but findings are mixed. Cannabis use is associated with improved, worsened, and no change in VL suppression.⁷¹⁻⁷³ Cannabis use is associated with improved, worsened, and no change in ARV adherence.^{72,74-81} In all of these studies, street cannabis use was examined rather than medical cannabis. *To our knowledge, no studies have examined how medical cannabis affects HIV outcomes. In the setting of rapidly increasing medical cannabis acceptance, it is critical to understand how cannabis affects HIV outcomes and psychological symptoms in PLWH.*

Summary: Neuropathic pain in PLWH is common and difficult to manage. Medical cannabis is an emerging new treatment, but gaps remain in our knowledge about its efficacy, mechanism, and effect on adverse events. To better understand how medical cannabis affects neuropathic pain in PLWH, we propose an observational cohort study to examine how medical cannabis affects pain, inflammation, and adverse events.

2) Study Design

2. A. Overview of study design: Our goal is to understand how medical cannabis affects self-reported pain, with attention to THC/CBD content, markers of inflammation, and adverse events. We will conduct an observational cohort study of 100 PLWH with neuropathic pain, active medical cannabis certification, and intent to use newly dispensed soft-gel capsule product from a medical cannabis dispensary. At baseline and over the following 14 weeks, participants will have 2 in-person visits and 14 web-based weekly questionnaires. Data sources will include questionnaires, medical

Table 4. Eligibility Criteria

Criterion	Source
Inclusion Criteria	
≥18 years old	SQ
Diagnosis of HIV	MR
Fluency in English	SQ
Active certification for medical cannabis	MR
No medical cannabis dispensed in 60 days or used within the previous 30 days	PR SQ
Intends to have new soft-gel capsule product dispensed at Vireo	MR PR
ICD-10 diagnosis code for neuropathic pain, OR Neuropathic pain in problem list of electronic medical record, OR Neuropathic pain per medical cannabis certification form, OR Neuropathic Pain Questionnaire- Short Form >0	MR MR MR SQ
Exclusion Criteria	
Inability to provide informed consent	SQ
Inability to complete 14 wks of study visits	SQ
Medical cannabis use within 30 days prior to enrollment	PR
Unique pain symptoms (e.g., multiple sclerosis, rheumatoid arthritis)	MR
Terminal illness	MR
Current or prior psychotic disorder	SQ

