Unregulated cannabis, opioid, cocaine, or benzodiazepine use in the past 30 d	SQ, U

records, pharmacy records, and blood and urine samples (see Table 8). Our primary independent variable will be the initial soft-gel product obtained

from the medical cannabis dispensary, and our primary outcome will be self-reported pain severity using the Brief Pain Inventory severity subscale.

2.A. Settings: Montefiore Health System (Montefiore) is the largest healthcare system in the Bronx, NY with 11 hospitals and over 200 community clinics. Directed by [name] (Primary Mentor), the Montefiore Medical Cannabis Program includes 2500 patients certified by 25 physicians; approximately 25% of patients are PLWH. Vireo is a medical cannabis company with dispensaries in 11 states; two dispensaries are located in the NYC area. As of August 2020, in NY, Vireo served over 30,000 unique patients. Vireo staff will refer potential participants to the study and facilitate study retention; recruitment will occur at dispensaries.

2.C. Research visits and data collection.

Eligibility criteria. *Inclusion criteria* are: 1) ≥ 18 years old; 2) diagnosis of HIV 3) fluency in English; 4) actively certified for medical cannabis (medical records); 5) no medical cannabis dispensed in 60 days or used within the previous 30 days; 6) intent to have new soft-gel capsule product dispensed at Vireo (PMP or medical record); 7) ICD-10 diagnosis code for neuropathic pain, OR neuropathic pain in problem list of electronic medical record, OR neuropathic pain per medical cannabis certification form, OR Neuropathic Pain Questionnaire Short Form >0 .

Exclusion criteria are: 1) inability to provide informed consent; 2) inability to complete 14 weeks of study visit; 3) medical cannabis use within 30 days prior to enrollment; 4) unique pain symptoms (e.g. multiple sclerosis, rheumatoid arthritis); 5) terminal illness; 6) current or prior psychotic disorder; 7) unregulated cannabis, opioid, cocaine, or benzodiazepine use in the past 30 days (self-report and urine drug screen); 8) dispensed opioids or benzodiazepines within 60 days of enrollment; 9) non-steroidal anti-inflammatory (NSAID) use within 7 days prior to enrollment; 10) steroid use within the past 14 days with duration of therapy >21 days; 11) COVID vaccination within 14 days of screening.

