Aims 1-4	Medical cannabis use	Initial soft-gel capsule dispensed at Vireo Certification for medical cannabis (date, doctor, conditions) All medical cannabis products dispensed (date, product, dose, amount dispensed) Self-reported medical and unregulated cannabis use (product, # of days used, route, dollar amount of unregulated cannabis purchased, ASI)	PR MR PR TQ
Primary outcome variables			
Aims 1, 4	Pain Severity	Brief Pain Inventory (BPI) Severity subscale ⁹⁰	TQ
Secondary outcome variable			
Aims 2, 4	Inflammatory cytokines	Pro-inflammatory cytokines (TNF α , IL-6) Anti-inflammatory cytokines (IL-4, IL-10)	B B
Aims 3, 4	Adverse events	VL, CD4 count AIDS Clinical Trial Group (ACTG Adherence) ⁹³ , Visual Analog Scale (VAS) ⁹⁴ ARVs dispensed Depression (Center for Epidemiological Studies-Depression Scale [CES-D])), Generalized Anxiety Disorder (GAD-7) ⁹⁶	B IQ PR IQ
Other measures			
Aims 1-4	Sociodemographics	Age, race/ethnicity, education, insurance, sex, gender	IQ
Aims 1-4	Pain characteristics	Brief Pain Inventory (BPI) Interference subscale ⁹⁰ Pain catastrophizing scale ⁹⁸ , Pain DETECT questionnaire ⁸⁴	IQ IQ
Aims 1-4	Pain treatment	Pain treatment (SSRIs, gabapentin, injections, physical therapy)	IQ/MR/PR
Aim 3	Substance use/disorder	Smoking (Fagerstrom test for nicotine dependence) ⁹⁹ , Alcohol Use Disorders Identification Test (AUDIT) ¹⁰⁰ , ASI ⁹⁷	IQ
Aim 3	HIV Risk Behaviors	HIV risk behaviors (HIV Risk-taking Behavior Scale ¹⁰¹⁻¹⁰³)	IQ
Aims 3, 4	Psychiatric symptoms	PTSD Checklist (PCL), ¹⁰⁴ Insomnia severity index, ¹⁰⁵	IQ
Aims 1, 3, 4	Quality of Life	Roland Morris Disability Questionnaire ¹⁰⁶ , Patient Reported Outcomes Quality of Life-HIV (PROQOL-HIV) ¹⁰⁷	IQ
Aims 1-4	Medical comorbidities	Comorbidities (obesity, cardiovascular disease, diabetes)	MR
Aims 1-4	Side effect vs benefit	Treatment Satisfaction Questionnaire for Medication (TSQM-9) ⁹¹	TQ
Aims 1-4	Urine cannabinoid	Urine GCMS for cannabinoids	

B=blood test; MR=Medical records; PR=Pharmacy records or Prescription Monitoring Program; IQ= in-person questionnaire; TQ=phone questionnaire; SSRI=selective serotonin reuptake inhibitor; TQ measures occur every week; IQ occurs at 0 and 14 weeks. B occurs at 0 at 14 weeks.

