4. Study records will be kept in locked files and/or within limited access, code-protected computer files, available only to the investigators and study personnel.
5. Publication or presentation of study results will not identify subjects by name.

In addition to addressing issues of confidentiality, it is crucial that we protect participants from emotional distress that may occur during research visits. All visits will occur in medical facilities. If emotional distress occurs during research visits an on-site physician will assess the patient. Per clinical judgment, the participant will either be referred to the Emergency Room or to their treating physicians the following day.

6.C. Potential benefits.

Neuropathic pain in PLWH is associated with poor HIV outcomes, including poor ARV adherence,³² virologic failure,³³ and poor retention in care.^{19,33} PLWH experience a high burden of pain,⁴⁻¹¹ and most commonly experience neuropathic pain.^{12,13} Medical cannabis has known analgesic properties in PLWH with neuropathic pain.^{24,25} Participants in our study will have been evaluated by their own physicians and deemed to be appropriate to receive medical cannabis based on those standards already. By participating in this study, they may experience benefit from medical cannabis use by experiencing improved pain. They may experience increased attention from research staff during the study period, resulting in improved pain, psychological, and HIV outcomes.

7) Data Analysis

7.A Data Analyses: *Intention-to-treat principle* will be used in primary analyses. If key variables (age, sex, medical comorbidities) are unequal among arms, we will conduct adjusted analyses. We will also conduct per-protocol analyses; medical cannabis use for at least 3 months of products will represent sufficient study participation.

Missing data: We will conduct multiple imputations using Markov Chain Monte Carlo imputation methods. Results from multiple imputed data sets will be pooled into a single dataset. We will compare statistical results using datasets with imputed values and the dataset that drops missing values.

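### The per-protocol rule in 7.A does not require use of the capsule type that defines the group, so the per-protocol comparison can carry the same switching dilution as the intention-to-treat one

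*Combined protocol and SAP*

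**What the plan says.** - **Group definition.** Section 2.A (overview): "Our primary independent variable will be the initial soft-gel product obtained" from the dispensary. Section 2.C gives two categories: "Main independent variable will be the soft gel capsule product dispensed at Vireo, including a 1) high THC capsule, or 2) high CBD capsule". There is no category for people who use both or change.
- **Design.** Section 2.A: "We will conduct an observational cohort study of 100 PLWH with neuropathic pain". Participants obtain their own products, and no section restricts later or additional ones.
- **Analysis sets.** Section 7.A says that the intention-to-treat principle "will be used in primary analyses". It adds per-protocol analyses, for which "medical cannabis use for at least 3 months of products will represent sufficient study participation". That is the whole rule: no capsule type, no minimum dose, nothing on switching, co-use or gaps.
- **Data available.** The measures table in 2.C lists "All medical cannabis products dispensed (date, product, dose, amount dispensed") from pharmacy or PMP records, together with self-reported use by product, days and route in the weekly questionnaire. Section 3.C confirms that the PMP extraction includes THC and CBD content in milligrams.
- **Dose-based exposure.** Section 2.C: "Other key independent variables will be cumulative THC and CBD taken (weeks 3-14, continuous measures"). Section 7.A, Aim 1: "We will repeat this model using alternative measures of medical cannabis (cumulative dose of THC and CBD"). Aims 2 and 3 carry the same sentence.

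**The concern.** H1 to H4 all concern THC versus CBD content. An intention-to-treat comparison by initial product is diluted if people later use the other product. A reader would normally expect a per-protocol analysis to show what happens among those who kept to the product that put them in their group. The rule in 7.A does not select those people.

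Take a participant who starts on the high-CBD capsule, moves to high-THC capsules in week 3 and continues to week 14. About 12 of that person's 14 weeks are on the opposite product. Counted over all medical cannabis use, the duration rule can be met, and under the 2.A definition the person belongs to the high-CBD group. If such people are kept in both analyses, agreement between the two says little about whether switching mattered.

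**Working it through.** **1. Does any reading of the rule remove switchers?** The phrase about products in the 7.A rule is unclear, so I took each plausible meaning in turn.

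- All medical cannabis products: a switch or addition passes.
- The study soft-gel capsules: both types are study capsules, so a switch between them still passes.
- A three-month supply: the type is again unspecified, so a mixed supply passes.

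Only a reading that inserts the words for the initial capsule type would exclude switchers, and the text does not contain them.

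**2. The plan's own figure.** Inputs from 3.A and Table 9: 40% vs 20% responders, 42 per group, two-sided 5%, ICC 0.4, stated power 84%. With 14 weekly measures (7.A, Aim 1) and a design-effect approximation, effective n per group = 42 × 14 / (1 + 13 × 0.4) = 588 / 6.2 = 94.8. The normal-approximation power for two proportions is then 0.858, within 2 points of the stated figure. This power is for the primary analysis. I use it below only as a scale.

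**3. Dilution if switchers are kept (one-way).** The documents give no switching rate, so s is an assumption. Suppose a fraction s of high-CBD starters respond at the high-THC rate. Then the high-CBD rate = 0.20(1 − s) + 0.40s.

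| s | High-CBD rate | Contrast with 40% | Power, same method |
|---|---|---|---|
| 0 | 20% | 20 points | 0.86 |
| 10% | 22% | 18 points | 0.77 |
| 20% | 24% | 16 points | 0.66 |
| 30% | 26% | 14 points | 0.54 |

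**4. Two-way switching.** If the same fraction of each group responds at the other product's rate, the contrast = 20(1 − 2s): 16, 12 and 8 points, with power 0.67, 0.44 and 0.22. If the fraction s of each group instead adds the other product and responds midway (30%), the contrast = 20(1 − s): 18, 16 and 14 points, with power 0.78, 0.67 and 0.56.

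**5. What a product-specific rule would do.** Removing a fraction s from each group leaves 42(1 − s) = about 38, 34 or 29. If removal is unrelated to outcome, the contrast stays at 20 points and power is 0.82, 0.77 or 0.72.

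That assumption is doubtful, so I also took an adverse case: only high-CBD starters switch, and all who switch are people who would not have responded on CBD.

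- Removed: the remaining high-CBD rate = 0.20 / (1 − s) = 22.2%, 25.0% or 28.6%, so the contrast is about 18, 15 or 11 points.
- Kept, and responding at 40%: the rate = 0.20 + 0.40s = 24%, 28% or 32%, so the contrast is 16, 12 or 8 points.

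Even in this case the product-specific rule is nearer to 20 points, but it does not get back there.

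**The case against.** The strongest reply is that the plan already analyses actual content. The Aim 1 to 3 models are repeated with cumulative THC and CBD dose over weeks 3 to 14, and Aim 4 pools dose from weekly questionnaires and PMP records. A high-CBD starter who moves to high THC in week 3 contributes that THC there. This stands as partial mitigation. Those models have their own confounding, however, and they do not define who is in the per-protocol set.

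Several stronger readings are tempting and are not supported:

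- *The rule expressly accepts any cannabis.* It does not say so. The wording is unclear, and the defect is that the capsule type is left unspecified.
- *Switchers certainly stay in their starting group.* This is inferred from 2.A. Section 7.A does not say how the per-protocol set is grouped, and its Aim 1 text speaks of those who use each capsule. That tension is a further reason for a written rule.
- *The per-protocol analysis does not test THC versus CBD content.* It tests a contrast that may be diluted; with one-way switching of 30%, 14 of 20 points remain.
- *The rule drops faithful users with short gaps.* Three calendar months are about 13.0 weeks of the 14 (3 × 365.25 / 12 / 7), but continuous use is not required in the text, and three months read as 12 weeks would leave a two-week margin.
- *The plan relies on per-protocol as its check on switching.* No section gives it that role.

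It is also fair to say that excluding switchers conditions on behaviour after baseline and can introduce selection bias. That stands, and it limits how the result may be interpreted.

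**Conclusion.** The point holds as a defect in a supporting analysis. The rule names no capsule type, the group is fixed by the initial product, and no section classifies switchers or dual users; applied as written, the per-protocol set can include people mainly exposed to the opposite product. The size depends entirely on a switching rate that the documents do not give. For one-way switching of 10% to 30%, with the plan's 40% and 20% applied to the product actually used, the 20-point contrast becomes 18 to 14 points. With two-way switching it becomes 16 to 8 points. With no switching it is unchanged. The primary intention-to-treat analysis is not altered by this point. The rule should be changed before the data are analysed.

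**What to change.** Replace the per-protocol sentence in 7.A with a product-specific definition:

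- the capsule type that defines the group was used in a prespecified number of the 14 follow-up weeks, stated in weeks, with a rule for gaps and late starts;
- no opposite-type medical cannabis product was dispensed or reported in that time;
- both conditions are derived from the PMP records and the weekly use questions.

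Report the number of switchers and dual users by initial product. Present the per-protocol result as a sensitivity analysis beside the intention-to-treat comparison and the cumulative-dose models.

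The cost is a few sentences in 7.A and some data derivation, with no new data collection. The per-protocol set will be smaller, and it may be selected on outcome because switching may follow poor relief; the plan should say that this will be stated when the result is interpreted.
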